#### **9.3.3.2 Symptomatic or Asymptomatic Diagnosis of COVID-19**

In a secondary analysis, in order to inform about the effectiveness to protect against asymptomatic and symptomatic infections, outcomes from the main analysis will be divided according to the symptoms recorded around the date of confirmed covid-19 in the patient PC eHR. Two effectiveness parameter, i.e. to protect against asymptomatic and asymptomatic infection, will be estimated separately for each vaccine. The date of the COVID cases will be the 1st date the sample was taken for testing.

Cases of **Asymptomatic** infection will be defined as a positive test without recorded symptoms in primary care  $\pm$ 14days, hospitalisations/Intensive care unit (ICU) or hospital diagnosis of the date the sample was taken). In asymptomatic analysis, symptomatic infections will participate as non-cases stopping at covid date.

Cases of **Symptomatic** infection will be defined as a positive test with recorded symptoms in primary care  $\pm$ 14days of the date the sample was taken, or linked Hospitalisations/Intensive care unit (ICU) admissions. In symptomatic analysis, asymptomatic infections will participate as non-cases stopping at covid date.

Note: In epidemiological vigilance protocols, among asymptomatic patients, isolation must be maintained till 10 days after the date when the sample was taken. For a sensitive approach we will broaden till 14 days in order to allow for delayed records in PC eHR.

\*Note: some misclassification may be present since patients with mild disease (mild symptoms) may never seek care that will be assumed as asymptomatic.

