## **8 Research Question and Objectives**

This study addresses the research question of whether vaccinations with new licenced COVID-19 vaccines, (Comirnaty, Moderna, AstraZeneca's and Janssen and subsequently

approved vaccines in the EU during the data collection), are effective in reducing the burden of COVID-19 in Spain in comparison with no vaccination periods.

**Primary objective** is to evaluate the effectiveness of each COVID-19 vaccine in reducing the covid-19 infections (confirmed through test and regardless the prognosis and clinical phenotype (i.e. whether symptomatic or asymptomatic, mild or severe).

**Secondary objectives** of this study will be splitting the effectiveness

- by the following outcomes:
  - asymptomatic (defined as a positive test (whether PCR or antigens) without recorded symptoms in primary care +/-14days of the date the sample was taken). Note: In epidemiological vigilance protocols, among asymptomatic patients, isolation must be maintained till 10 days after the date when the sample was taken.
  - symptomatic (defined as positive test (whether PCR or antigens) with recorded symptoms in primary care or Hospitalisations/Intensive care unit (ICU) admissions +/-14days of the date the sample was taken (or at anytime linked with the test result))
  - Hospitalisations/Intensive care unit (ICU) admissions for COVID-19 at anytime linked with the test result or within +/-14days of the date the sample was taken (if hospitalisation was recorded in primary care clinical profile)
  - All-cause mortality as a recorded death with COVID 19 listed as an underlying cause of death on cause-of-death registers, or a death during a hospitalisation, with COVID-19 as a listed diagnosis, or a death within a specified time period (e.g., 28 days) after a diagnosis or hospitalisation for COVID 19.
- over clinically meaningful subgroups (old people; patients with cardiovascular disease, diabetes, or chronic pulmonary disease, chronic renal impairment, treated cancer, patients with a history of transplantation, Down Syndrome found linked with the prognostic of the covid-19 infection; as well as smoking, males and obesity suspected linked with the prognosis in some studies)
- along the time since complete vaccination (up-to 3 months, 6 months and ever after).

A feasibility evaluation will be conducted before the start of the study to evaluate the availability of key data elements and the appropriateness of the study design.

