## **9.2 Setting**

This study will be conducted in Spain where the 1st COVID-19 vaccine was included in public campaigns after approval by the European Commission from 21st December 2020. The eligibility criteria will change over time according to prioritised vaccination groups as follows in Figure 1:

Due to the potentially changing incidence of COVID-19 over time and prioritised vaccination groups, comparisons within the study periods and prioritised criteria will be established as much as possible.

According to the 1st prioritized groups (see Figure above), the **study period** will begin on the 21st of December 2020. The end of study period will be the last date of data received at the start of the data collection. Since the vaccines start to request the vaccination for young people (for example: Pfizer requested to the FDA to expand use of its Covid-19 vaccine to adolescents ages 12 to 15 on 9th April 2021), no age restriction will be applied for the source population.

No sex restriction will be applied.

In BIFAP, as per quality and quantity criteria for research, and in order to ensure precise anamnesis, only those clinical histories considered up-to-standard are included in pharmacoepidemiological studies.

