### 9.3.1 Exposure Assessment and Time At Risk

Data will be collected from BIFAP database with data from Spain (described in [Data Sources](#)).

**Inclusion criteria** to the Source population: up-to-standard,  $\geq 1$  year baseline information in January 2021 in BIFAP. The last date of filling all the inclusion criteria will be the inclusion date. No restriction to age or sex will be applied.

**Exclusion criteria:** Patients with prevalent COVID vaccinations or infections ever before (i.e. washout period) the inclusion criteria will be excluded.

**Stop date:** the last moment of the following criteria will define the stop date to contribution: covid-19 infection, death, loss to follow-up and end of study period (the last date available in the data source at data collection).

**Exposure assessment:** The 1st vaccination recorded after the inclusion date will be the time zero for patients included in the vaccinated group, as explained in section 'Definition of Time Zero' [9.1.1.4](#).

From the source population, 10 individuals unvaccinated on or before time zero of the vaccinated pair (10:1) will be randomly selected among those with similar birth cohort, sex and region (matched criteria). Patients included in the comparison group, may be vaccinated later during their follow-up period and then contribute to the vaccinated group (from the date of vaccine administration ahead; i.e. time zero for the vaccinated group).

\*Note: All individuals vaccinated during their follow-up contribution will be included in the vaccinated group. While, a random selection of the unvaccinated individuals will be included as unvaccinated group.

The date and type of vaccine administered will be collected from the **Table of Vaccine** from BIFAP data model. In particular, Covid-19 vaccinations will be ascertained from official covid-19 vaccination registries and provided by the regional governments. The coding system is not known yet. The feasibility analysis will include an evaluation of the coding type, whether or not vaccines are recorded according to standardised system or not. We expect that either ATC07 (J07????) or National Code (CNF [Código Nacional de

Farmacia]) specific for pharmaceuticals in Spain is available for all vaccines administered.

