### **9.3.3 Outcome Assessment**

Outcomes will be assessed during the follow-up period (Section 9.3.1). Multiple effectiveness outcomes associated with vaccination for COVID-19 are proposed in this protocol, as the severity of COVID-19 and its complications may vary widely. The severity of COVID 19 illness has been shown to vary from asymptomatic to life-threatening.

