The last date available in the data source at data collection will be the end of the Study time period.

\*The study population is defined in terms of Exposure (instead of Disease/Indication)

‡Duration of follow-up: Inclusion date and stop date to follow-up define the Duration of follow-up.

Section 5: Exposure definition and measurement	Yes	No	N/A	Section Number
5.1 Does the protocol describe how the study exposure is defined and measured? (e.g. operational details for defining and categorising exposure, measurement of dose and duration of drug exposure)				9.3.1
5.2 Does the protocol address the validity of the exposure measurement? (e.g. precision, accuracy, use of validation sub-study)				9.1.1.3
5.3 Is exposure categorised according to time windows?				9.1.1.4
5.4 Is intensity of exposure addressed? (e.g. dose, duration)				9.1.1.4
5.5 Is exposure categorised based on biological mechanism of action and taking into account the pharmacokinetics and pharmacodynamics of the drug?				9.1.1.4
5.6 Is (are) (an) appropriate comparator(s) identified?				9.3.1;9.1.1.4*

Comments:

\*We have discarded to select other control groups due to the reason explained in 9.1.

Section 6: Outcome definition and measurement	Yes	No	N/A	Section Number
6.1 Does the protocol specify the primary and secondary (if applicable) outcome(s) to be investigated?				8; 9.3.3
6.2 Does the protocol describe how the outcomes are defined and measured?				8; 9.3.3
6.3 Does the protocol address the validity of outcome measurement? (e.g. precision, accuracy, sensitivity, specificity, positive predictive value, use of validation sub-study)				8; 9.1.1.2

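### Cases sampled in the last 14 days of data lack the full window for symptom records, so a symptomatic case first recorded after the data cut is counted as asymptomatic

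*Protocol*

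**What the plan says.** The asymptomatic outcome is defined by an absence. In Section 9.3.3.2 an asymptomatic "infection will be defined as a positive test without recorded symptoms in primary care" around the sample date, and without a hospital or ICU record. Section 8 gives the same rule for primary-care symptoms: "without recorded symptoms in primary care +/-14days of the date the sample was taken". Section 9.3.3.2 notes a 10-day isolation rule and then lengthens the window: "For a sensitive approach we will broaden till 14 days in order to allow for delayed records in PC eHR". Cases are dated at the first sample.

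The end of counting is set elsewhere. Section 9.2: "The end of study period will be the last date of data received at the start of the data collection". The criteria for the stop date in Section 9.3.1 include "end of study period (the last date available in the data source at data collection". The checklist in Annex 1 (comments to its Section 4) repeats it: "The last date available in the data source at data collection will be the end of the Study time period". Section 9.3.3 adds: "Outcomes will be assessed during the follow-up period (Section 9.3.1".

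Nothing in the protocol requires 14 days of data after the sample, ends accrual earlier for this split, or leaves a case with a cut-off window unclassified. The only misclassification that Section 9.3.3.2 admits is that of mild cases who never seek care. The limitations in Section 9.9 do not mention truncation at the data cut.

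**The concern.** The two rules do not fit together. The classification needs 14 days of records after the sample, and the accrual rule accepts cases that cannot have them. This differs from ordinary censoring. When the record has not yet arrived, the case is not set aside: it becomes an event in the asymptomatic analysis and a non-event, stopped at its COVID date, in the symptomatic one.

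The asymptomatic outcome then contains some symptomatic cases. If the vaccine protects better against symptomatic infection, mixing the two moves asymptomatic VE toward symptomatic VE. The split is a named secondary objective, estimated separately for each vaccine. Fully vaccinated follow-up lies late in the calendar, so the period at least 15 days after full vaccination, which the main analysis targets, carries the largest share of the error.

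**Working it through.** The protocol states no figure on this point, so there is none to reproduce. The mechanism follows from the text; the size below is an illustration.

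**Share of calendar time affected**
- Study start 21 December 2020 (Section 9.2). Data assumed to end on 30 June or 31 July 2021, following the start and end of data collection in Section 6.
- Whole study: 14/192 = 7.3% (30 June) or 14/223 = 6.3% (31 July).
- Fully vaccinated period: general vaccination from 22 March 2021 (Section 9.5), plus 21 days between doses (the shorter of the two intervals in Section 9.3.1), plus 15 days, gives 27 April. Counting both end dates: 14/65 = 21.5% or 14/96 = 14.6%.

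**Share of fully vaccinated person-time affected**
Under linear uptake from 27 April, with T days elapsed to the data end, the last 14 days hold w = 1 - ((T - 14)/T)².
- 30 June, T = 64: w = 1 - (50/64)² = 0.39.

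**Share of symptomatic cases missed in those 14 days**
Let q be the share of symptomatic cases whose first record comes after the sample, with lag uniform over 1-14 days. A case sampled j days before the cut is missed if its lag exceeds j. The mean over j = 0 to 13 of (14 - j)/14 is 0.536. So m = 0.536 × q:
- q = 10%: m = 0.054
- q = 50%: m = 0.268

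**Effect on asymptomatic VE**
Let s be the symptomatic share of infections in the unvaccinated, a = 1 - s and x = w × m, with constant incidence and the same error in both groups:

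observed RR = [a(1 - VEa) + s·x·(1 - VEs)] / [a + s·x]

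Assume VEs = 90%, VEa = 50%, s = 50-70%, data to 30 June.
- Low end (s = 0.5, q = 10%, x = 0.021): (0.25 + 0.5 × 0.021 × 0.1)/(0.5 + 0.5 × 0.021) = 0.492, VE 50.8%.
- High end (s = 0.7, q = 50%, x = 0.104): (0.15 + 0.7 × 0.104 × 0.1)/(0.3 + 0.7 × 0.104) = 0.422, VE 57.8%.

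| Data end | T | w | Observed asymptomatic VE, true 50% | Observed, true 70% |
|---|---|---|---|---|
| 30 June 2021 | 64 | 0.39 | 50.8-57.8% | 70.4-73.9% |
| 31 July 2021 | 95 | 0.27 | 50.6-55.8% | 70.3-72.9% |
| 10 October 2021 | 166 | 0.16 | 50.3-53.7% | 70.2-71.8% |

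The October row is 22 March + 21 + 181 days, the first day on which the longest follow-up band of Section 9.1.1.4 could be reached from a 22 March start.

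**The case against.** **Symptoms are often recorded by the time of the test.** The window looks both ways, and Section 9.9 links test-seeking to symptom severity. This stands. A reader might infer that all late symptomatic cases become asymptomatic. The definition does not support that: only a case whose first symptom or hospital record falls after the cut is affected.

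**The bias could be put higher.** If half of the symptomatic cases in the last 14 days were unrecorded (m = 0.5), the same formula gives up to 62.5% for a true 50%. Under a uniform 1-14 day lag that needs q = 0.5/0.536 = 93%, so nearly every symptomatic person would have no record until after sampling. Nothing in the protocol suggests this.

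**Other results are safe.** A reader might extend the problem to the calendar-month strata. Section 9.7.4.1 plans those for the primary analyses, whose outcome is any laboratory-confirmed infection, and that outcome does not depend on the split. A reader might also see bias in symptomatic VE. Pairs share time zero; if the loss of symptomatic events is equal in both groups, it mainly costs precision.

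**Equal error should cancel.** It does not for the asymptomatic outcome, because the added cases come from an outcome with a different VE.

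**The horizon may differ.** Section 9.1 expects data every two months, and later deliveries could complete earlier windows and reduce the share affected. The abstract gives the population as December 2020 till April 2021. Were that a case cut-off, extraction at the end of June would leave 61 days after 30 April and the problem would vanish. The phrase describes the population, however, and Sections 9.2 and 9.3.1 set the end of study as the last date of data.

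**A statistical analysis plan could hold the date rule.** It could, and none is shown here. But the protocol fixes both the window and the end date, and the error comes from those two together.

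**Conclusion.** The concern holds in this limited form. As written, a symptomatic case sampled in the final 14 days and first recorded after the data cut is classed as asymptomatic. When symptomatic VE exceeds asymptomatic VE, the effect on asymptomatic VE is upward. The illustrated bias runs from under 1 to about 8 percentage points with data to the end of June 2021 and a true value of 50%, and shrinks with later data or a smaller gap between the two VEs. Confidence in the mechanism is high and in the size low: the recording lag, the share recorded after sampling, the symptomatic share, both VEs, uptake and incidence are all assumptions. It concerns two secondary outcomes, is cheap to prevent, and should be corrected before the analysis.

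**What to change.** Add to Section 9.3.3.2: for the symptomatic and asymptomatic analyses only, accrual of cases and person-time ends 14 days before the last date on which the region's linked primary-care, laboratory and hospital records are all complete; the final 14 days serve only to classify earlier cases. The date should be set by region, because the abstract expects data to arrive from the regions at different times, and on completeness rather than receipt, because the hospital source in Section 9.4 includes discharge diagnoses. Leave the primary analysis on the full period. State that April 2021 in the abstract is not the case cut-off, or reconcile it with Sections 9.2 and 9.3.1.

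Every counted case then has its full primary-care window. The cost is a sentence, a date shift in the program, and the last 14 days of follow-up for these two secondary outcomes: about 6-7% of calendar time since 21 December 2020, and about 15-22% of the fully vaccinated calendar span.

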### **9.3.3.3 Severe COVID-19 Hospitalisation for COVID-19**

In a secondary analysis, the outcome will be incident covid-19 infections resulting in an admission or discharge diagnosis to hospital (inpatient record) or intensive care unit as the setting of care. Admissions will be identified through linked (at anytime) with the test result or within  $\pm$ 14days of the date the sample was taken (if hospitalisation was recorded in primary care clinical profile). Those type of identification will depend on the region providing the data to BIFAP. If not available for all regions, restriction to regions will be performed.

The date of the outcome will be the admission date.

In that analysis, remaining non-severe covid-19 infections will participate as non-cases stopping at covid date.

### **9.3.3.4 COVID-19–Specific Mortality**

The data availability on the cause of death will depend on the region providing the data to BIFAP, thus the primary outcome of COVID-19–specific mortality will have the following hierarchical definition

- A recorded death with COVID-19 listed as an underlying cause of death on cause-of-death registers
- Death during a hospitalisation, with COVID-19 as a listed diagnosis
- Death within a specified time period (e.g., up-to 8 weeks [73]) after a diagnosis or hospitalisation for COVID-19

The date of the outcome will be the date of death.

### **9.3.3.5 All-Cause Mortality**

Cause-of-death information in BIFAP may be lacking depending on the region providing data; therefore, all-cause mortality will be used as a secondary outcome. All-cause mortality will be defined as a recorded patient death in primary care, or hospital records during the outcome ascertainment period of up-to 8 weeks after the date of the COVID date for main analysis (the 1st date the sample was taken for testing as recorded in the lab registries linked to PC eHR if available). The date of the outcome will be the date of death.

### **9.3.4 Covariate Assessment**

In order to control for measurable confounders in the analysis, the following variables will be collected: lifestyle characteristics (BMI, smoking alcohol use), comorbidities, comedICATIONS, and health care utilisation prior to or at time zero and updated every 21 days and at every change in the exposure period (i.e. when receiving D1, D2) at the patient level. Given that risk factors for COVID-19 infection are not currently well understood [30], we will measure covariates that are classically controlled for in pharmacoepidemiologic research and leaves room for the inclusion of risk factors yet to be determined.

As explained in [Data source](#), clinical events will be collected by using the International Classification of Primary Care (ICPC) and the International Classification of Diseases 9th Revision (ICD-9) medical terms (6,7).

The following variables will all be assessed as last status before time zero:

- Smoking status
- Body mass index
- Alcohol use

The following comorbidities (and others that may be shown to be associated with COVID-19 prognosis) will be assessed ever before time zero and updated:

- Diabetes mellitus (types 1 and 2)
- Hypertension record
- Cardiovascular disease
- Cerebrovascular disease
- Chronic respiratory disease
- Chronic kidney disease
- Chronic liver disease
- Cancer

- Immunodeficiencies including Human immunodeficiency virus and other immunosuppressing conditions
- Autoimmune disorders

Comedication use will be assessed through pharmacy dispensing and primary care physician prescribing records by ATC. Considered comedications may be indicative of comorbidities placing patients at higher risk or markers of health care-seeking behaviour and utilisation and may serve as markers of patients' history of other infections or be risk factors for severe COVID-19 disease themselves. The following comedications will be assessed during the year before time zero and updated:

- Antibiotics
- Antiviral medications
- Corticosteroids
- Non-steroidal anti-inflammatory drugs
- Other Analgesic
- Psychotropics
- Statins
- Immunosuppressant medication use

Health care utilisation in the year before time zero and updated will be evaluated as measures of health care-seeking behaviour, overall health status, and access to health care. Additionally, short-term health care utilisation in the 2 weeks before and including time zero and updated will be recorded separately, as short-term markers of current health status may influence individuals' vaccination decisions. Considered variables will include the following:

- Primary care utilisation (number of visits to PC)
- Influenza vaccination (number in the previous 5 years)
- Other vaccinations (number in the previous 5 years)
- COVID-19 tests (total number)

Frailty has been demonstrated as a confounder of vaccine-outcome associations in older adults [5,6,9]. Additional personal characteristics demonstrated to be associated with frailty [6,31,32] should be included as confounding factors, and may include the following:

[figure not shown]
- Wheelchair use
- Home hospital bed
- Paralysis
- Parkinson's disease
- Skin ulcer

- Weakness
- Stroke/brain injury
- Ambulance transport
- Dementia
- Difficulty walking
- Home oxygen
- Rehabilitation care
- Psychiatric illness
- Sepsis
- Heart failure
- Podiatric care
- Bladder continence
- Diabetes complications
- Arthritis
- Coagulation deficiencies
- Vertigo
- Lipid abnormalities

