## **9 Research Methods**

### **9.1 Study Design**

An observational cohort study of people prioritized for covid-19 vaccination will be implemented to allow for the estimation of effect measures on the absolute scale

(incidence difference) (e.g., time point-specific difference) [10] and relative scale (e.g., time point-specific risk ratios, hazard ratios, and vaccine effectiveness measures). The occurrence of covid-19 infection among unvaccinated and vaccinated patients will be compared as defined below.

This study primarily describes an approach to the retrospective collection of data to using BIFAP data (and linked registry by patient's level) after the necessary data have accumulated (real-time; expected every 2 months starting in 21st December 2021).

The choice of an exchangeable comparator group is a key factor in ensuring a valid study design and addressing confounding. In the current protocol, individuals not yet receiving COVID 19 vaccines will be pooled for a random selection among those with matched criteria to the vaccinated individuals. We have discarded to select the following control groups due to the reason explained below:

- Identified at receipt of a different vaccine such as influenza: the period of influenza vaccination (September-December) seems to be fewer circulation covid-19 since fewer incidences were reported. Thus, they may not be comparable
- During a general practitioner visit: will not be as frequent or representative or a normal non-pandemic situation when people are able to visit the health setting without any restriction. Thus, they may not be comparable
- Choosing a fixed time unit (weeks for instance) to create a series of nested cohorts, each starting at each new time unit [20,21]. Similar to the selected option, this one is valid and although more precise it is more complicated to implement. Also, the variance estimation would need to be adjusted accordingly (e.g., by bootstrapping) because individuals are allowed to contribute to multiple study cohorts [22].

The inclusion and exclusion criteria for the study cohort and thus for the selection of comparative groups are described in the following sections.

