#### **9.7.3.2 Adjustment for Confounding**

Backward stepwise selection method will be used to identify variables associated with each outcomes according to a level of significance ( $p\text{-exit} \geq 0.1$ ,  $p\text{-entry} < 0.05$ ) for inclusion or exclusion, that could confound the effectiveness estimates and thus adjust the final models.

Confounders will be measured at baseline and updated before each vaccine dose is administrated or every 28 days (in order to update the collection of confounders during the follow-up of both, vaccinated and unvaccinated patients). The adjusted vaccine effectiveness for all the outcomes will be estimated as 1 minus the adjusted HR.

Adjusted time-specific RDs (e.g., RD at 3, 6, 9, 12 months after time zero) will also be tested [38]

Patients receiving one type of vaccine who receive later a dose of another COVID-19 vaccine, will be considered switcher from the date that the last dose was received and analysed as switchers, since such censoring/switch can be informative. Among switchers, each combination of vaccines will be analysed separately.

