Patterns of routine health care delivery and utilisation may be disrupted during the COVID-19 pandemic as patients and providers forgo or delay routine preventive, elective, or non-emergency care. These disruptions in health care may result in under-

ascertainment of important patient comorbidities in existing health care databases during periods of disruption.

In order to conduct a valid study and address potential confounding, the eligibility criteria of the study will be restricted relative to the approved indications of the vaccines. Therefore, the results of this study may not be generalisable to the general population but to the restricted population.

With the introduction of a new vaccine, there is the potential for rapidly changing herd immunity in the population. This study is not designed to assess overall and indirect effects of vaccination with COVID-19 vaccines.

Comparative analyses may not be possible in every setting if confounding is deemed to be insurmountable. However, descriptive information about vaccine recipients and crude incidence rates may still be informative and meaningful, even without calculation of vaccine effectiveness measures.

The capture of over-the-counter medications, potentially indicative of short-term disease status (e.g., painkillers, cough medicines, and fever reducers) may not be captured reliably.

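### The one-year look-back for primary care visits and comedication falls almost wholly in the pandemic for general-population vaccinees, and no pre-pandemic window is set for these two covariate families

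*Protocol*

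**What the plan says.** Protocol 9.3.4 gives visit counts a baseline window of one year: "Health care utilisation in the year before time zero and updated will be evaluated as measures of health care-seeking behaviour". The same sentence gives them two further roles, as markers of overall health and of access to care. Comedication has the same window: "The following comedications will be assessed during the year before time zero and updated". The text treats it partly as a marker of comorbidity and partly as a marker of care-seeking.

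Other covariates in 9.3.4 have different windows:
- Influenza vaccinations and other vaccinations are counted over five years.
- COVID-19 tests are a total count.
- Comorbidities have no limit on look-back.
- A short window is added: "short-term health care utilisation in the 2 weeks before and including time zero and updated will be recorded separately".

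Two other sections comment on health care use in the pandemic. Section 9.1 rejects the GP visit as the event for selecting comparators because such visits "will not be as frequent or representative or a normal non-pandemic situation". Section 9.9 concedes: "Patterns of routine health care delivery and utilisation may be disrupted during the COVID-19 pandemic". The consequence it names is under-recorded comorbidity. It does not mention visit counts or comedication.

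Inclusion (9.3.1) requires one "year baseline information in January 2021 in BIFAP".

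**The concern.** Section 7 regards confounding as probably the greatest threat to validity. Visit counts and comedication are among the main tools in 9.3.4 for adjusting for care-seeking, health status and access. If they are read from a year in which attendance was restricted, two things can go wrong.

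- **Lost ranking.** People who normally attend often and people who rarely attend may look alike. Adjustment then removes only part of the confounding.
- **Changed meaning.** Section 9.9 says that people who keep their distance or confine themselves may be both more often vaccinated and less often infected. In a pandemic year, few visits may mean low care-seeking or it may mean caution. One coefficient cannot separate the two.

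Whatever is left over stays in every adjusted VE. The disruption noted in 9.9 is applied there to comorbidities, which have the longest look-back and so are least exposed. The two families with the one-year window are not discussed.

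**Working it through.** The Protocol states no figure on this point, so there is nothing to reproduce. The check is date arithmetic followed by an illustration of scale.

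**1. Share of the one-year window inside the pandemic**

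Inputs: earliest time zero 21 December 2020 (9.2); start of general vaccination 22 March 2021 (9.5). The documents give no date for the start of disruption, so I assume a range from 1 January to 1 April 2020.

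Share = days from the later of (window start, disruption start) to time zero, divided by days in the window.

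| Time zero | Disruption from 1 Jan 2020 | from 1 Mar 2020 | from 1 Apr 2020 |
|---|---|---|---|
| 21 Dec 2020 | 355/366 = 97% | 295/366 = 81% | 264/366 = 72% |
| 22 Mar 2021 | 100% | 100% | 355/365 = 97% |
| 30 Apr 2021 or later | 100% | 100% | 100% |

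Section 9.1.1.3 says the first priority groups will not be studied, so the rows from 22 March 2021 are the relevant ones for most of the cohort.

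**2. Same calculation for the five-year vaccination counts** (5 × 365.25 = 1826.25 days)

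- Time zero 21 December 2020: 264/1826.25 = 14.5% to 355/1826.25 = 19.4%.
- Time zero 22 March 2021: 355/1826.25 = 19.4% to 446/1826.25 = 24.4%.

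These counts are therefore mostly pre-pandemic.

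**3. Does updating help?**

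Section 9.3.4 has covariates "updated every 21 days and at every change in the exposure period", while 9.7.3.2 says: "Confounders will be measured at baseline and updated before each vaccine dose is administrated or every 28 days". The 21-day and 28-day intervals disagree and must be reconciled. Under either, updating moves the window later, further into the pandemic. The two-week window is wholly within it.

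**4. Scale, illustration only**

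Let r be the residual confounding hazard ratio left after adjustment. Then observed HR = true HR × r, and the shift in VE = true HR × (1 − r).

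Both inputs to r are assumptions, not figures from the Protocol: confounding alone gives HR 0.85, and the one-year covariates capture 40% to 70% of it on the log scale. Then r = 0.85^0.6 = 0.907 to 0.85^0.3 = 0.952, so 1 − r = 0.093 to 0.048.

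| True HR | Source | Observed VE | Shift (points) |
|---|---|---|---|
| 0.05 (VE 95%) | Table 1, highest expected | 95.2% to 95.5% | 0.2 to 0.5 |
| 0.331 (VE 66.9%) | Table 1, lowest expected | 68.5% to 70.0% | 1.6 to 3.1 |
| 1.00 (VE 0%) | no effect | 4.8% to 9.3% | 4.8 to 9.3 |

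The shift is proportional to the true HR. It is small where the vaccine works well and largest where it does little, such as the 14 days after the first dose or, if protection wanes, beyond 180 days after the second. The sign is also assumed: 9.9 describes biases in both directions.

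**The case against.** The other side has a good case on several points.

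- **The Protocol does not contradict itself.** A reader might infer that it calls its own covariate year unrepresentative. Section 9.1 speaks of GP visits as the event for selecting comparators. It says nothing of the covariate window or of comedication, and rejecting visits for selection is compatible with adjusting for visit counts.
- **The one-year window is not the only measure.** A reader might infer that care-seeking is measured in that year alone. The covariates are updated, and the five-year vaccination counts, arguably the most direct marker of vaccine-related behaviour, are mostly pre-pandemic. Comorbidities have no look-back limit.
- **Some of the problem is designed out.** Matched pairs share time zero, birth cohort, sex and region, so a general fall in visits affects both groups. Section 9.7.4.1 plans an influenza-vaccinated subgroup aimed at this kind of confounding, and 9.9 discloses the disruption.
- **Recent contact may be the better measure.** Behaviour and health around vaccination in 2021 may be closer to pandemic-year contact than to 2019 contact. Nothing in the documents settles this.

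The first two points stand in full and limit the finding to two covariate families. The third stands in part: a shared calendar time removes the average fall in visits but does not restore lost or altered ranking between individuals, and the subgroup analysis does not correct the main estimate. The fourth is a reason to keep the one-year window; it is not a reason to rely on that window alone.

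**Conclusion.** The point holds for visit counts and comedication only. For general-population vaccinees, 97% to 100% of their look-back year is pandemic-era, given an assumed start of disruption between 1 January and 1 April 2020, and no earlier window is set for them. Some residual confounding may follow.

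Its size cannot be derived from the documents. A reader might infer from the illustration that VE is inflated by 5% to 9%. That is not supported: both inputs are assumed, the figure applies only at a true VE of zero, and it describes the whole residual, not the part that a 2019 window would remove. At the highest and lowest effectiveness in Table 1 the same assumptions give about 0.2 to 3 points. Nor do the documents support a general conclusion that behavioural confounders are poorly measured, because the vaccination counts are mostly pre-pandemic.

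This is a cheap improvement to the adjustment set. It matters most for the periods in which VE is expected to be low, and it is not an error that invalidates the main analysis.

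**What to change.** In 9.3.4:
1. Add primary care visit counts and comedication for calendar 2019 as time-zero covariates for everyone with a 2019 record, and state what coverage of 2019 counts as having a record.
2. Keep the existing one-year and two-week windows as measures of recent health and contact.
3. Give people without a 2019 record a separate category, in the way 9.7.5 already handles missing BMI and smoking.

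In 9.7.4, add the main adjusted VE restricted to people with a 2019 record as a sensitivity analysis. While editing, reconcile the 21-day and 28-day update intervals in 9.3.4 and 9.7.3.2.

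Cost: a few more covariates from the same database, which the five-year vaccination counts already presuppose reaches back that far. The downside is that inclusion needs only one year of record. Someone who just meets that in January 2021 has a record starting in January 2020 and no 2019 value. How many such people there are is not stated and should be reported.
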